Primary Outcome Measures:	Retrospective and prospective data will be collected, that include: Overall participant survival, evaluated based on chronological age at time of death or at conclusion of study, whichever occurs first.
Secondary Outcome Measures:	Retrospective and prospective data will be collected, that include: The rate of change (i.e., slope) in neurocognitive functioning over the duration of follow-up will be determined; and will also be compared to available published natural history data. This analysis will be conducted separately for each of the two disease sub-types: infantile and juvenile. The primary neurocognitive measure for both pediatric groups is age-equivalent scores of the Bayley Scales of Infant and Toddler Development for expressive communication, receptive communication, fine motor skills and gross motor skills. The secondary neurocognitive measure for both pediatric groups is standard and age-equivalent scores of the Vineland Adaptive Behavior Scales for communication, daily living skills, socialization and motor skills, and the Vineland composite standard score.
Statistical Considerations (sample size and analysis plan):	The sample size (number of enrolled subjects) will be large enough to detect trends and differences. The primary analysis for Syner-G therapy will use the intention-to-treat (ITT) population and evaluate overall survival based on chronological patient age. Median survival will be compared to previously reported natural history studies of infantile and juvenile gangliosidoses. For rate of change in neurocognitive functioning over the duration of follow-up, using general estimating equations (GEE) and an exchangeable working correlation structure, variance estimation for confidence intervals and p-values will take into account the possible correlated nature of multiple measurements on the same individual. Supportive analyses will include evaluation using the per-protocol (PP) population. Subgroup analyses: analyses will be repeated separately among the infantile and juvenile forms of both GM1 and GM2 gangliosidosis.
Sponsors (federal, state, foundation and industry support):	National Institutes of Health (NIH)

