A survey based study of 316 patients with infantile GM2 gangliosidosis (survey-based data from 92 patients, data from 103 patients in the National Tay-Sachs and Allied Diseases patient advocacy group's database, and 121 patients reported in the literature), it was noted that in infantile GM2 gangliosidosis, the most common onset symptoms were developmental delay, startle-response and hypotonia.⁹ Among the 92 patients surveyed, there were few differences noted in phenotype between infantile Tay-Sachs disease and infantile Sandhoff disease, although a tendency was observed for visual problems, seizures and movement abnormalities to occur earlier in the patients with Tay-Sachs disease.⁹ As the disease advanced, seizure management often became the primary focus of clinical care.⁹

In the study by Maegawa et al. the mean onset of symptoms in juvenile GM2 gangliosidosis was reported as 5.3 ± 4.1 years, with gait disturbances, incoordination, speech difficulties and developmental delay being the most common symptoms noted at onset.¹¹ Neuropathy and psychiatric disturbances were found to be more common in patients with juvenile Sandhoff disease compared to juvenile Tay-Sachs disease.¹¹ In patients with juvenile Sandhoff disease, sleep problems, diarrhea and constipation were observed to be more common than in the patients with juvenile Tay-Sachs disease.¹¹ Dysphagia, sphincter incontinence and sleep problems were more common at the time of symptom onset in Tay-Sachs disease.¹¹ But this study found no other statistically significant differences between the patients with juvenile Tay-Sachs disease compared to patients with juvenile Sandhoff disease.¹¹

1.1.4 Natural history survival data in infantile and juvenile gangliosidosis. The study by Bley et al. showed the median age of death in the infantile form was 47 months.⁹ The case histories of 155 patients with juvenile GM2 gangliosidosis that were reviewed by Maegawa et al. were found to have a median survival of 14.5 years.¹¹ Nearly half of the patients died within the first decade of life, and roughly 25% of the patients lived into their late teens.¹¹ No statistically significant differences were found between the patients with Tay-Sachs disease and those with Sandhoff disease.¹¹

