There is limited human experience in the use of miglustat in children (especially those less than 4 years of age); as well as known risks of peripheral neuropathy, diarrhea and weight loss. Thrombocytopenia is a known side effect, so prior to surgery or invasive procedures, the child will require a CBC to ensure that the procedure can be safely performed.

Miglustat is in pregnancy risk category C in the USA. There are no adequate, well controlled studies of miglustat in pregnant women. In female rats given miglustat at doses of 20,60,180 mg/kg/day beginning 14 days before mating and continuing through day 17 gestation, decreased live births, decreased birth weight and complete litter loss was observed in the mid- to high-dose groups.²⁶ In the pregnant rats in the mid- to high-dose groups, delayed parturition and dystocia were also observed.²⁶

10.10 Dosing guidelines. Subjects with body surface area (BSA) < 0.73 m² will receive the goal dose of 100 mg miglustat three times daily, or the maximum dose tolerated up to 100 mg miglustat three times daily.

Rationale: studies of miglustat in infants and young children with gangliosidosis diseases have shown safety and tolerability. (References: (1) Maegawa GH, van Giersbergen PL, Yang S, Banwell B, Morgan CP, Dingemans J, Tiffet CJ, Clarke JT. Pharmacokinetics, safety and tolerability of miglustat in the treatment of pediatric patients with GM2 gangliosidosis. *Mol Genet Metab.* 2009 Aug;97(4):284-291; (2) Bembi B, Marchetti F, Guerci VI, Ciana G, Addobbati R, Grasso D, Barone R, Cariati R, Fernandez-Guillen L, Butters T, Pittis MG. Substrate reduction therapy in the infantile form of Tay-Sachs disease. *Neurology.* 2006 Jan 24;66(2):278-280; (3) Maegawa GH, Banwell BL, Blaser S, Sorge G, Toplak M, Ackerley C, Hawkins C, Hayes J, Clarke JT. Substrate reduction therapy in juvenile GM2 gangliosidosis. *Mol Genet Metab.* 2009 Sep-Oct;98(1-2):215-224.)

The safety, tolerability and pharmacokinetic study cited above (by Maegawa et al. 2009) showed safety and tolerability of miglustat in eleven children with GM2 gangliosidosis. In this study six of the patients had infantile phenotype (with ages ranging between 1 year and 5 years and BSAs ranging between 0.4 m² and 0.7 m²), and five patients had the juvenile phenotype (with ages ranging between 10.1 years and 20 years and BSAs ranging between 0.8 m² and 1.8 m²).

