13.2 Study population. Study population will be any patient with an infantile or late-infantile/juvenile gangliosidosis disease.

13.3 Sample size. A total of 30 infants or children:

- 5 patients with infantile Tay-Sachs disease
- 5 patients with juvenile Tay-Sachs disease
- 5 patients with infantile Sandhoff disease
- 5 patients with juvenile Sandhoff disease
- 5 patients with infantile GM1 gangliosidosis
- 5 patients with juvenile GM1 gangliosidosis

13.4 Subject recruitment. Subjects will be recruited from the investigators' clinical practice and through the Lysosomal Disease Network. This clinical trial will be posted on ClinicalTrials.gov and this may serve to recruit patients to the study.

13.5 Subject screening. Eligibility will be assessed during a baseline evaluation and will include confirmation of gangliosidosis disease via mutation analysis and tissue (e.g. leukocyte) ascertainment of level of hexosaminidase or β -galactosidase enzyme activity.

13.6 Prior and concomitant therapy. Subjects may have had previous therapies for gangliosidosis. If subjects are taking miglustat and/or pyrimethamine, and/or are on a ketogenic diet at the time of screening, they will be allowed to continue these therapies and will be allowed to participate in the Syner-G study.

13.7 Inclusion criteria. Subjects will be eligible to participate in the study if all of the following criteria are met: 1) confirmed diagnosis of infantile or juvenile GM1 or GM2 gangliosidosis via mutation analysis and tissue enzyme activity analysis (e.g. leukocyte activity of β -hexosaminidase A, including percent activity contributed from both α -subunit and β -subunits) or tissue β -galactosidase enzyme activity; 2) subjects must be age 0 - 17 years at time of enrollment; and 3) subjects and their caregivers must work closely with their University of Minnesota ketogenic diet team, and with their local ketogenic diet team, which must include a ketogenic dietician and a neurologist trained in the ketogenic diet.

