18.0 Data Analysis

18.1 Subject populations for analysis:

- Intention-to-treat Population (ITT): All subjects who initiate any portion of the treatment regimen in association with this study
- Per-protocol Population (PP): Includes all subjects who initiate treatment and are compliant with at least 75% of prescribed drug doses of miglustat, and at least 3:1 ketogenic diet.
- Safety population: All subjects who receive any amount of the combination treatment regimen. Due to the nature of a combination treatment, multiple groups may be identified, should partial adherence be observed.

18.2 Sample size determination. The sample size for the study was determined primarily by feasibility due to the extremely rare nature of the disease. There are two distinct sub-types to be evaluated: infantile and juvenile. Analysis will be based on variability estimates from published natural history studies^{8,11,19} of the infantile form and juvenile form, and correlation between baseline and annual follow-up for up to 4 years.

18.3 Statistical analysis. Descriptive analyses of baseline characteristics and outcomes will include means, standard deviations, medians, and ranges for continuous variables and frequencies for categorical variables. Treatment compliance for each group will also be evaluated. All analyses will be conducted separately for the two disease sub-types – infantile and juvenile – due to the highly heterogeneous patient groups.

The primary analysis for Syner-G treatment regimen will use the intention-to-treat (ITT) population and evaluate overall survival. This will be evaluated based on chronological age at time of death or conclusion of study (whichever occurs first), and compared to available natural history data. Median survival will be compared to previously reported natural history studies of infantile⁹ and juvenile¹¹ forms. Infantile median survival was estimated at 47 months based on data from the National Tay-Sachs and Allied Diseases database for patients born after 2000.⁹ Median survival for the juvenile form was estimated at 14.5 years.¹¹

A secondary endpoint will be the rate of change (i.e., slope) in neurocognitive functioning over the duration of follow-up, compared to available natural history data. This analysis will be conducted separately for each of the two sub-types: infantile and juvenile. The primary

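### The primary survival comparison counts years lived before enrolment as survival on the regimen, and it names no estimator or censoring rule

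*Combined protocol and SAP*

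**What the plan says.** The Synopsis defines the primary outcome as overall survival, "evaluated based on chronological age at time of death or at conclusion of study, whichever occurs first". Sections 12.1, 13.1 and 18.3 repeat this for the ITT population; in Section 18.3 survival is "evaluated based on chronological age at time of death or conclusion of study (whichever occurs first), and compared to available natural history data". Sections 12.1 and 18.3 name the comparators: an infantile median of 47 months, and for the other sub-type "Median survival for the juvenile form was estimated at 14.5 years". Section 18.3 analyses the two sub-types separately.

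Three provisions determine who contributes:

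- Section 13.7: "subjects must be age 0 - 17 years at time of enrollment". One range serves both sub-types.
- Section 18.1 defines ITT as "All subjects who initiate any portion of the treatment regimen in association with this study", so every child is alive at entry.
- Section 13.6 and the notes to the schedule in Section 17 admit children already on the component therapies or on Syner-G.

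For survival, Section 18.3 names no estimator, test, interval or rule for children alive at study conclusion. GEE is named only for the neurocognitive slopes. Section 18.4 deals with non-survival outcomes and loss to follow-up, and does not mention entry age.

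**The concern.** A child who enrols at a given age could not have died earlier and still be in the study. If survival is counted from birth without allowing for this, the years before entry are death-free by construction, yet they enter the estimate as survival on treatment. An infantile-form child enrolled after 47 months, or a juvenile-form child enrolled after 14.5 years, has passed the benchmark on the day of entry.

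Such entry ages are plausible. In the earlier paediatric GM2 miglustat study described in Section 10.10, "six of the patients had infantile phenotype (with ages ranging between 1 year and 5 years" and "five patients had the juvenile phenotype (with ages ranging between 10.1 years and 20 years".

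The fault is not age as a time scale, since the benchmarks are ages too. It is the missing entry time. The unnamed estimator adds a second problem: Kaplan-Meier from birth favours the regimen, whereas a plain median of age at death or study end treats living children as if they had died and can err either way.

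The trial has one arm, so this external comparison is its only survival evidence. A median above the benchmark, or one not reached, could be read as benefit when there is none.

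**Working it through.** **Inputs from the plan.** Medians of 47 months and 14.5 years (12.1, 18.3); 15 children per sub-type, from six groups of five (13.3); entry at 0-17 years (13.7); rolling enrolment over five years (Synopsis). The plan has no power or event calculation to reproduce.

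**Assumptions.** The documents give neither Syner-G entry ages nor a full natural-history curve. I take no treatment effect and Weibull age at death with the stated median m and shape k from 1.5 to 3, so the cumulative hazard is H(t) = ln 2 × (t/m)^k.

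**Step 1: one child.** Given alive at age E, the median age at death is (m^k + E^k)^(1/k).

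- Infantile, E = 36 months: k = 3 gives (103,823 + 46,656)^(1/3) = 53.2 months; k = 1.5 gives 66.2. The benchmark is 47.
- Infantile, E = 12 months: 47.3-51.0 months. E = 60 months: 68.4-85.2 months.
- Juvenile, E = 10.1 years: 16.0-19.7 years, against 14.5. E = 15 years: 18.6-23.4 years.

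**Step 2: already past the benchmark at entry.** With uniform entry over the Section 10.10 ages (juvenile capped at 17):

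- Infantile: (60 − 47)/(60 − 12) × 15 = 4.1 children.
- Juvenile: (17 − 14.5)/(17 − 10.1) × 15 = 5.4 children.

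If entry is skewed young, these fall to about 1 and 2.

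**Step 3: whole trials.** There were 3,000 null trials per setting, n = 15, follow-up uniform on 0-5 years, and entry ages uniform, skewed young, or uniform then thinned by survival. Entries are the share of trials with the median above the benchmark, counting not reached as above. The fair reference is about 50%. These are not type I error rates, because the plan sets no test.

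| Entry age | Kaplan-Meier from birth | Kaplan-Meier, delayed entry | Raw median |
|---|---|---|---|
| Infantile 6-18 months | 52-63% | 50-56% | 0-1% |
| Infantile 6-36 months | 58-82% | 49-57% | 2-15% |
| Infantile 12-60 months | 85-100% | 49-63% | 37-90% |
| Juvenile 4-10 years | 73-83% | 65-77% | 0% |
| Juvenile 4-17 years | 83-99% | 49-57% | 0-14% |
| Juvenile 10.1-17 years | 99-100% | 70-87% | 42-94% |

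For juvenile entry at 4-17 years the from-birth median was not reached in 34-73% of trials. The 4-10 year row is uninformative, because almost every result above the benchmark is a median not reached. In the last row even delayed entry is conditional on reaching 10.1 years, so its median is not comparable with 14.5.

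**Step 4: size in time units.** A separate large-sample run used k = 2-3 and uniform entry. Juvenile entry at 3-17 years gave a from-birth median of 16.9-19.4 years, against 14.45-14.95 with delayed entry. Infantile entry at 0.5-4 years gave 4.24-4.65 years, against 3.92-3.97; the benchmark is 47/12 = 3.92.

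**Step 5: juvenile curve.** Section 1.1.4 says: "Nearly half of the patients died within the first decade of life, and roughly 25% of the patients lived into their late teens". The Weibull curves leave 67-80% alive at 10 years, which does not fit. A curve forced through that description, with S(10) = 0.52-0.55, S(14.5) = 0.50 and S(18.5) = 0.25, puts 100% of null trials above the benchmark for entry at 4-17 years.

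**Step 6: does conditioning on entry age work?** Take expected deaths as the sum over children of H(exit age) − H(entry age). Observed/expected was about 1.0 in every setting. The exact one-sided 5% test rejected in 0-3.6% of null trials.

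**The case against.** The best reply is that the text does not forbid delayed entry, that overall survival with a median ordinarily implies censoring, and that the benchmark cohorts may be selected in a similar way. The plan describes those cohorts as surveys, an advocacy-group database and literature cases (1.1.4, 12.1), but does not show whether their medians carry the same truncation. The net bias is therefore uncertain, and the simulation treats the benchmarks as exact. That much stands. It does not rescue a primary analysis that leaves open a choice able to decide its conclusion, and cancellation cannot be assumed.

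The size is also open to challenge:

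- It depends on unknown entry ages. With entry more strongly skewed to young ages (Beta(1,3)), the from-birth shares are 73-89% for infantile 12-60 months and 72-84% for juvenile 4-17 years, so the lower ends in the table are not bounds. They remain well above 50%.
- The oldest ranges come from an 11-patient study whose juvenile ages extend beyond this trial's limit.
- The raw-median column tests a strained reading of the plan, although one sentence would exclude it.

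Finally, Sections 13.1 and 18.3 already repeat the analyses by GM1 and GM2. The remaining point there is narrower: the pooled primary analysis sets 10 GM1 subjects among 30 against GM2 medians, and no GM1 benchmark is given.

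**Conclusion.** The concern holds, and it should be fixed before the survival data are analysed. As written, the study median depends on how old children were at entry and on unstated handling of survivors, as well as on the regimen. With Kaplan-Meier from birth the error favours Syner-G. It is negligible for infantile entry at 6-18 months and large for infantile entry at 1-5 years or juvenile entry up to 17. Eligibility does not confine entry to the range where the bias is small.

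The direction follows from the design alone. The percentages rest on the assumed Weibull shapes, entry-age patterns and follow-up, and on benchmarks free of similar truncation, so they are illustrative.

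**What to change.** In Sections 12.1, 13.1 and 18.3, and in the Synopsis to match:

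1. State that children alive at study conclusion are right-censored. Keep age as the time scale, and enter each child into the risk set at the age of first study treatment, or at enrolment if already on Syner-G.
2. Make the main comparison observed versus expected deaths after entry (one-sample log-rank with an exact Poisson interval), taking expected deaths from the natural-history curve conditional on each child's entry age. Use left-truncated Kaplan-Meier as description only: with juvenile entry at 4-17 years it fell to zero while older children were still under observation in 8-20% of null trials. Report entry ages and the number past the benchmark at entry.
3. Apply the GM2 curves to GM2 subjects. Report GM1 separately, or label use of a GM2 curve as an assumption. First reconcile the juvenile figures in Section 1.1.4. Also settle whether 47 months is a median age at death (1.1.4) or a median survival (12.1, 18.3), since the two need not define the same curve.
4. As a secondary point, Sections 16.2 and 21.2 do not provide for vital status after withdrawal. State that it is collected by telephone to study close for all ITT subjects unless consent to contact is withdrawn.

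The cost is wording, reading published curves, and a few calls; no new visits or subjects. The price is a less favourable and less precise estimate. Expected deaths are about 5.5-10 infantile and 1.5-4.6 juvenile; with GM2 only (n = 10, uniform entry) they are 3.8-6.6 and 1.2-3.1. Zero deaths reaches one-sided 5% only if exp(−expected) ≤ 0.05, that is, expected deaths of at least ln 20 = 3.0. The juvenile result should therefore be reported as an estimate with its interval.

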Protocol Number:	LDN 6729
Protocol Title:	Synergistic Enteral Regimen for Treatment of the Gangliosidoses (Syner-G)
Study Chair:	[name]
Statistician:	[name].
Consortium:	Lysosomal Disease Network
Participating Sites:	University of Minnesota
Activation Date:	02/24/2016
Sample Size:	A total of 30 infants or children: 
 • 5 patients with infantile Tay-Sachs disease • 5 patients with juvenile Tay-Sachs disease • 5 patients with infantile Sandhoff disease • 5 patients with juvenile Sandhoff disease • 5 patients with infantile GM1 gangliosidosis • 5 patients with juvenile GM1 gangliosidosis
Target Enrollment Period:	Rolling enrollment of patients with infantile or juvenile gangliosidosis over the next five years; whenever possible, making one yearly visit to the University of Minnesota
Study Design:	Interventional study
Therapeutic Agent:	Miglustat
FDA IND Status:	IND 127636 Active
Phase:	Phase II
Methodology:	Combination enteral therapy
Study Design:	Single arm, open-label treatment study
Study Duration:	5 Years
Primary Study Objective:	To assess the impact of Syner-G therapy on overall survival in patients with infantile and juvenile forms of gangliosidosis
Secondary Study Objective:	To evaluate effects of Syner-G therapy in pediatric gangliosidoses patients on their neuro-developmental status
Study Population and Main Eligibility/Exclusion Criteria:	
Study Population: Any infant or juvenile patient with a gangliosidosis disease.
 
Inclusion Criteria:
 
 1.) Subjects must have a documented infantile or juvenile gangliosidosis disease. 2.) Age: 17 years or less at time of enrollment. 3.) Subjects and their caregivers must work closely with their University of Minnesota ketogenic diet team, and with their local ketogenic diet team, which must include a ketogenic dietician and a neurologist trained in the ketogenic diet. 
Exclusion Criteria:
 
 1.) A desire to not participate. 2.) Children with severe renal impairment will not be enrolled in this study. 3.) Post-pubertal females who are pregnant, or who are unwilling to use highly-effective methods to prevent pregnancy, will be excluded from this study. 4.) Breast-feeding females will be excluded from this study. 5.) Subjects who have an allergy to miglustat or any of the

	components within the drug product will be excluded from this study.

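### The primary survival endpoint merges ages at death with ages at study end and has no censoring rule, estimator or fallback, so the juvenile median against 14.5 years mainly reflects entry age and follow-up

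*Combined protocol and SAP*

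**What the plan says.** The Synopsis (Primary Outcome Measures) defines the primary outcome as overall survival, "evaluated based on chronological age at time of death or at conclusion of study, whichever occurs first". Sections 12.1, 13.1 and 18.3 repeat this; in 18.3 survival is "evaluated based on chronological age at time of death or conclusion of study (whichever occurs first". Sections 12.1 and 18.3 add the comparison: "Median survival will be compared to previously reported natural history studies". The benchmarks in 18.3 are "Infantile median survival was estimated at 47 months" and "Median survival for the juvenile form was estimated at 14.5 years".

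Four other statements bear on what can be observed:
- Entry age (13.7): "subjects must be age 0 - 17 years at time of enrollment". No expected distribution of entry age is given.
- Accrual (Synopsis): "Rolling enrollment of patients with infantile or juvenile gangliosidosis over the next five years". The study duration is also five years.
- Follow-up: the schedule in section 17.0 runs visits to year 5, while 18.2 refers to "correlation between baseline and annual follow-up for up to 4 years".
- Group size (13.3): three juvenile and three infantile strata of five, so 15 children per sub-type, set by feasibility (18.2).

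The plan does not say that a child alive at study end is censored. It names no survival estimator, confidence interval or test for survival. Section 18.4 deals with missing non-survival outcomes and with loss to follow-up by carrying the last observation forward; it does not cover censoring of survival.

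**The concern.** An age at death and an age at study end are different kinds of observation. The first is an event. The second is only a lower bound on age at death. Section 18.3 puts both into one variable and takes a median. On that wording, a living 8-year-old contributes 8 years of survival, and the result moves with entry age and follow-up whether or not the regimen works.

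Adding censoring is necessary but does not fully repair the comparison. A Kaplan-Meier median exists only if the estimated curve falls to 0.5, so the more deaths are prevented, the less often the planned summary can be computed. The plan does not say what is reported then.

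The primary objective is at stake. The headline juvenile figure could fall below 14.5 years, exceed it or be missing, for reasons unrelated to treatment.

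**Working it through.** **Reproducing the plan's figure.** The only stated figure is the sample size: 6 × 5 = 30, of which 3 × 5 = 15 are juvenile. It agrees. No alpha, power, effect size or event count is given, so there is no power calculation to reproduce.

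**Step 1: which juveniles can be observed at 14.5 years.** Entry age needed = 14.5 − follow-up.
- 5 years of follow-up: 14.5 − 5 = 9.5 years
- 4 years: 14.5 − 4 = 10.5 years
- 2.5 years (the mean if accrual is even and the study closes at year 5): 14.5 − 2.5 = 12.0 years

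A child enrolled between 14.5 and 17 is past the benchmark on the first day.

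**Step 2: literal median if nobody dies.** For symmetric distributions this is close to median entry age plus median follow-up.

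| Assumed entry age (uniform) | Follow-up 0-5 years | Five full years each |
|---|---|---|
| 3-12 years | 7.5 + 2.5 = 10.0 | 7.5 + 5 = 12.5 |
| 5-15 years | 10 + 2.5 = 12.5 | 10 + 5 = 15.0 |
| 3-17 years | 10 + 2.5 = 12.5 | 10 + 5 = 15.0 |

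The first column lies wholly below 14.5. The second lies on both sides of it. The regimen is the same in every cell.

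**Step 3: literal median if the regimen does nothing.** Simulation used 15 juveniles and Weibull survival with cumulative hazard H(a) = ln 2 × (a/14.5)^k, k from 1.5 to 2.5, conditional on being alive at entry. On 0-5 years of follow-up the median drops by only 0.2-0.3 years from the no-death values. With five full years each it drops by up to about 1.3 years. The differences between entry-age scenarios (2.5 years) and between follow-up scenarios (2.5 years) are larger.

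**Step 4: Kaplan-Meier on age, censored, with delayed entry.** Share of simulated trials with an estimable juvenile median, 0-5 years of follow-up, across the three entry ranges and both shapes:
- no effect: about 47-81%
- post-entry hazard halved: about 23-53%
- no deaths: 0%, which needs no assumption, because the curve stays at 1

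**Step 5: censoring without delayed entry.** Children must survive to enrol. If the time before enrolment is counted as time at risk, the Kaplan-Meier median exceeds 14.5 years under no treatment effect in 24-91% of runs. This used entry uniform on 2-17 or 5-17 years or four years after onset, and shapes 1.5 and 3.2. The error can therefore also favour the regimen.

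**Step 6: infants.** Entry age needed to pass 47 months = 47 − 12 × follow-up in years: 47 − 60 = −13 months with 5 years, 47 − 48 = −1 with 4 years, and 47 − 30 = 17 months with 2.5 years. Every survivor with four or more years of follow-up passes the benchmark.

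**Step 7: the assumed curve against the documents.** Share dead by age 10 = 1 − exp[−ln 2 × (10/14.5)^k], which is 33% for k = 1.5 and 24% for k = 2.5. Section 1.1.4 reports close to half. The percentages in steps 3 and 4 illustrate the behaviour of the measure; they do not forecast this trial.

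**The case against.** The strongest defence is that the literal reading is uncharitable. The endpoint is called overall survival, and stopping at whichever of death or study end comes first is normal time-to-event language, so a statistician would censor without being told. That may be the intention, but the plan does not say so. Censoring alone also leaves the delayed-entry bias and the missing fallback.

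A reader might infer three stronger things that the documents do not support:
- **That a juvenile group with no deaths must fall short of 14.5 years.** Entry is allowed to age 17 and no entry-age distribution is given; step 2 shows medians of 15.0 years with five years each.
- **That follow-up averages 2.5 years.** This needs even accrual and closure at year 5. The Synopsis is compatible with that, but the visit schedule to year 5 and the mention of up to four years in 18.2 leave it open.
- **That the primary comparison cannot show success in juveniles.** A median that is not reached can still be informative: if children are at risk at 14.5 and the curve there is above 0.5, the median exceeds the benchmark, and a lower confidence limit can also be compared. Under delayed entry, older entrants supply that risk set.

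It is also fair to say that choosing another lead summary is a design judgement in a small feasibility-sized study. The reason to change is that the planned summary becomes estimable less often as the regimen works better.

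**Conclusion.** The concern holds in this form: the primary endpoint lacks a censoring rule, an estimator and a fallback, and the juvenile median against 14.5 years reflects age at enrolment and length of follow-up more than treatment. That a median does not exist when no child dies is certain. The direction of error on the literal reading is not settled; it depends on entry ages and follow-up that the documents do not give. The simulated sizes rest on 15 juveniles, uniform entry ages, 0-5 or five years of follow-up, and a Weibull curve with median 14.5 years that has fewer early deaths than section 1.1.4 describes. The infantile comparison is less exposed, and is largely unaffected if follow-up is four years or more. Because this is the primary analysis, it should be corrected before the data are analysed.

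**What to change.** Change the Synopsis, 12.1, 13.1 and 18.3 as follows.

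1. State that children alive at study end or last contact are censored at their last known-alive age. Estimate survival by Kaplan-Meier on the age scale, with each child entering the risk set at the age of enrolment or treatment start (choose one and say which), and give a confidence interval.
2. Make the lead comparison, by sub-type, observed deaths against expected deaths. For each child, expected deaths = H(age at death or last contact) − H(age at entry), with H the cumulative hazard from the natural-history curve; sum over children. For example, under the step 3 curve with k = 1.5, a child followed from 8 to 10.5 years contributes 0.427 − 0.284 = 0.143. Every child counts, whatever the follow-up.
3. Report the median only if reached. Otherwise give its lower confidence limit, and the survival estimate at the benchmark age where children are at risk there.

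A fixed two-year survival proportion should not be the primary summary: with follow-up uniform on 0-5 years, 2/5 = 40% of children would lack two years.

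The cost is wording in four places and analysis code, using dates that the endpoint already needs. There are three drawbacks. The headline is no longer one median beside 47 months and 14.5 years. Expected deaths must be read from the published curves, since the documents give only medians and rough fractions. Those figures are for GM2 only, so GM1 children need their own reference or separate descriptive reporting. Precision also stays limited. Under no effect, simulations gave about 2 to 7 juvenile deaths; with none observed, the exact 95% upper limit is −ln(0.025) = 3.69 deaths, so the observed-to-expected ratio excludes 1 only if more than 3.69 deaths were expected.
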